11.5 Adverse Event Recording Period

AEs will be monitored and recorded in the study database from the time of first exposure to the therapy in this study (i.e., the start of the first dosimetry infusion). AEs with an onset date prior to the first exposure to an investigational product will not be recorded, except in the case of clinically significant worsening of the AE during the specified AE monitoring time frame.

12.0 DATA AND SAFETY MONITORING PLAN

Institutional support of trial monitoring will be in accordance with the Fred Hutch/University of Washington Cancer Consortium Institutional Data and Safety Monitoring Plan. Under the provisions of this plan, Fred Hutch Clinical Research Support (CRS) coordinates data and compliance monitoring conducted by consultants, contract research organizations, or Fred Hutch employees unaffiliated with the conduct of the study. Independent monitoring visits occur at specified intervals determined by the assessed risk level of the study and the findings of previous visits per the institutional DSMP.

In addition, protocols are reviewed at least annually and as needed by the Consortium Data and Safety Monitoring Committee (DSMC), Fred Hutch Scientific Review Committee (SRC) and the Fred Hutch /University of Washington Cancer Consortium Institutional Review Board (IRB). The review committees evaluate accrual, adverse events, stopping rules, and adherence to the applicable data and safety monitoring plan for studies actively enrolling or treating subjects. The IRB reviews the study progress and safety information to assess continued acceptability of the risk-benefit ratio for human subjects. Approval of committees as applicable is necessary to continue the study.

The trial will comply with the standard guidelines set forth by these regulatory committees and other institutional, state and federal guidelines.

13.0 DATA MANAGEMENT/CONFIDENTIALITY

Research data will be recorded in a study-specific, password protected database using a unique study ID for each patient to assure patient confidentiality. Data from source documents will be transcribed into this database. Source documents are documents where patient data are recorded and documented for the first time. They include, but are not limited to, hospital records, clinical and office charts, laboratory notes, memoranda, quality of life assessments, pharmacy dispensing records, recorded data from automated instruments, copies of transcriptions that are certified after verification as being accurate and complete, X-rays, patient files, and records kept at the pharmacy, laboratories, and medico-technical departments involved in the clinical trial. There will be no case reports forms (CRFs) used for this trial.

The investigator will ensure that data collected conform to all established guidelines. Each subject is assigned a unique subject number to protect subject confidentiality. Subjects will not be referred to by this number, by name, or by any other individual identifier in any publication or external presentation. The licensed medical records department, affiliated with the institution where the subject receives medical care, maintains all original inpatient and outpatient chart

documents. Patient research files will be maintained under control of the Principal Investigator and/or study team and kept in a locked office or file room within a secure building. Access to the study database will be restricted by electronic password protection and restricted access to computers (i.e., locked offices).

14.0 STATISTICAL CONSIDERATIONS

This is a pilot study of medically less fit adults with newly diagnosed AML or analogous myeloid neoplasm to evaluate the feasibility of randomized assignment to either lower-intensity or higher-intensity chemotherapy in a 1:1 fashion.

14.1 Treatment allocation

Treatment will be allocated based on patient preference. If agreeable to randomization, participants will be allocated to either lower-intensity G-CLAM or higher-intensity G-CLAM in a 1:1 ratio using a computer-generated random list of numbers. Randomization will occur in blocks of 4. Participants not agreeable to randomization will be allocated to lower-intensity G-CLAM or higher-intensity G-CLAM as per subject's preference.

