6.0 TREATMENT PLAN

This study is a single-center, open-label randomized pilot study of lower-dose vs higher-dose G-CLAM for medically less fit adults with newly diagnosed AML or analogous myeloid neoplasms at the Fred Hutchinson Cancer Research Center/University of Washington/Seattle Cancer Care Alliance.

Study Overview

In this pilot study, patients meeting the inclusion/exclusion criteria and their primary oncologists are asked whether or not they would agree to participate in the randomized treatment assignment (APPENDIX D). Patients agreeable to randomization will be assigned in a 1:1 ratio to the higher-dose G-CLAM arm or the lower-dose G-CLAM arm that utilizes lower doses of cladribine, cytarabine, and mitoxantrone. For those who wish to not be randomized, the reasons to decline randomization will be recorded, and patients will be allowed to receive the treatment intensity of their choosing. Patients will receive higher-dose or lower-dose G-CLAM as follows:

Treatment arm	G-CSF (SC, D0-D5)	Cladribine (IV 2h, D1-D5)	Cytarabine (IV, D1-D5)	Mitoxantrone (IV, D1-D3)
Higher-dose G-CLAM	300 or 480 µg*	5 mg/m ²	2,000 mg/m ² **	18 mg/m ²
Lower-dose G-CLAM	300 or 480 µg*	2 mg/m ²	100 mg/m ² ***	6 mg/m ²

*Dosing based on patient weight: <76kg vs. ≥76 kg; **over 2 hours; ***over 1 hour

After study enrollment, patients will receive a first cycle of G-CLAM on one of the designated treatment arms. Post-induction bone marrows will be reassessed upon blood count recovery or between day Days +28 to +35 after start of chemotherapy, whichever occurs first. If a response other than a measurable (“minimal”) residual disease-negative (MRDneg) CR is achieved, the patient will receive re-induction with G-CLAM at the same dosing. Patients who achieve a morphologic CR or CR with incomplete count recovery (CRi) with up to 2 courses of higher-dose G-CLAM or up to 6 courses of lower-dose G-CLAM can receive consolidation therapy with G-CLA (i.e. mitoxantrone omitted; up to 4 cycles with high-dose G-CLA and up to 12 cycles of low-dose G-CLA).

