APPENDIX D: PATIENT PREFERENCE FOR TREATMENT ASSIGNMENT SURVEY

We would like to understand whether patients and their doctors are comfortable letting a “coin flip” decide whether lower- or higher-intensity chemotherapy is used. We also want to understand how you made this decision, and why. Please answer the following questions:

1) Preference for treatment assignment

After thinking about this study and discussing it with your doctor(s), how do you prefer to be treated?

- I am willing to let a coin flip (i.e. computer program) decide whether I receive lower- or higher intensity chemotherapy
- I would like to make the decision whether I receive lower- or higher-intensity chemotherapy myself
 - My preference is to receive **lower**-intensity chemotherapy
 - My preference is to receive **higher**-intensity chemotherapy

2) How did you make this decision?

- I made the final decision about which treatment I would receive
- I made the final decision of my treatment after seriously considering my doctor's opinion
- My doctor and I decided together which treatment is best for me
- My doctor made the decision after seriously considering my opinion
- My doctor made the final decision about which treatment I would receive

3) Which factors were most important for you in making this decision?

Patient name/signature: _____

Date: _____

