APPENDIX E: PHYSICIAN PREFERENCE FOR TREATMENT ASSIGNMENT SURVEY

We are conducting a study to better understand whether patients and their doctors are comfortable letting a “coin flip” decide whether lower- or higher-intensity chemotherapy is used. We would like to ask you two questions about your preference for treatment assignment and which factors are important for making this decision. It should take about 5 minutes. There are no foreseeable risks to your participation. There is no payment for taking part in this research and your participation is voluntary. Choosing not to participate will not incur a loss of benefits to which you are otherwise entitled. You will not directly benefit from taking this survey, but we hope we can better understand how decisions about treatment intensity are made. We will ask you to provide your name and we will link your responses to similar questions we are also asking the patient you are treating. However, your name will remain confidential and if results of this study are published we will not use your name. If you have questions about this study, please contact [name] MD at [contact]. If you have questions about your rights as a research participant, you can contact [name], Director of the Institutional Review Office, Fred Hutchinson Cancer Research Center, at [contact].

1) Preference for treatment assignment

After thinking about this study and discussing it with the patient, how do you prefer for the patient to be treated.

- I am willing to randomize the patient to lower- or higher intensity chemotherapy and they agree
- I am willing to randomize the patient to lower- or higher intensity chemotherapy but the patient would prefer to choose treatment themselves and they chose:
 - Lower-intensity chemotherapy
 - Higher-intensity chemotherapy
- Neither I nor the patient want to proceed with randomization and the following person chose the treatment arm:
 - Myself
 - The patient

2) Which factors were most important for you in making this decision?

- The patient did not want to be randomized (did not like the idea of a “coin flip”)
- The patient thought one treatment arm was better than another
- I thought one treatment arm was better than another

- I thought the patient was too frail/unfit for the higher intensity treatment and that this arm would be too toxic
- I was concerned the lower intensity arm would not be efficacious enough
- Other, please explain:

Physician name: _____

Date: _____

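### Section 14.1 discloses one fixed block size of 4 in an open-label, single-centre study: up to about 31% of randomized assignments could be known in advance to a fully informed observer

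*Combined protocol and SAP*

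**What the plan says.** Section 14.1 allocates patients who agree to randomization "in a 1:1 ratio using a computer-generated random list of numbers" and adds "Randomization will occur in blocks of 4". It names no stratification factor, no holder of the list and no variation in block size.

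Section 6.0 describes the setting: "This study is a single-center, open-label randomized pilot study of lower-dose vs higher-dose G-CLAM". It also says that patients and "their primary oncologists are asked whether or not they would agree to participate in the randomized treatment assignment".

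Refusal does not end participation. Section 14.1 says "Participants not agreeable to randomization will be allocated to lower-intensity G-CLAM or higher-intensity G-CLAM as per subject's preference". The Appendix D survey asks the patient: "After thinking about this study and discussing it with your doctor(s), how do you prefer to be treated". One of the reasons that Appendix E offers the physician depends on the arm: "I thought the patient was too frail/unfit for the higher intensity treatment and that this arm would be too toxic".

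Under section 14.3.1 the primary conclusion rests on how many of 50 patients agree, with 26 or more counted as feasible. Section 14.4 compares early death and MRDneg CR between arms among randomized patients and may close an arm on the result. Under 14.3.1, early closure of an arm also leads to the conclusion that randomization is not feasible.

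**The concern.** In a permuted block of 4, once two patients have gone to one arm, the rest of the block must go to the other. With one list, one centre and visible treatment, the sequence can in principle be reconstructed from the published block size and the earlier randomized assignments. Restricting access to the list does not prevent this.

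The usual worry is selection into arms. Here there is a second one, because agreement to be randomized is itself the primary endpoint. A physician who expected the next slot to be the arm thought unsuitable for a patient could discourage agreement, and one who expected the suitable arm could encourage it. The first would lower the observed proportion and the second would raise it. Either would also affect which patients enter each arm in the between-arm comparison of section 14.4.

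**Working it through.** **Inputs.** Block size 4, ratio 1:1 and no strata (14.1); up to 50 patients (14.2); feasible if at least 26 of 50 agree (14.3.1). The number randomized is unknown in advance. I use 26, the threshold, and 30, which is 60% of 50.

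**1. The plan's own figures.** With X binomial (50, p), P(X ≥ 26) is 0.902 at p = 0.60, 0.057 at 0.40 and 0.0009 at 0.30. The stated 90%, 6% and <1% reproduce. They assume that agreement does not depend on the next slot.

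**2. Certain assignments in blocks of 4** (six equally likely orders of two and two).
- Positions 1 and 2 are never certain.
- Position 3 is certain if the first two match: probability 2/6 = 1/3.
- Position 4 is always certain.
- Share in complete blocks: (1/3 + 1)/4 = 33.3%.
- 26 randomized (6 blocks plus 2): 6 × 4/3 = 8.0, and 8.0/26 = 30.8%.
- 30 randomized (7 blocks plus 2): 7 × 4/3 = 9.3, and 9.3/30 = 31.1%.

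**3. Best guess.** The chance of being right by position is 1/2, 2/3, 2/3 and 1. The sum is 2.833, so complete blocks give 2.833/4 = 70.8%. At 30 randomized: (7 × 2.833 + 1/2 + 2/3)/30 = 21.0/30 = 70.0%. With no information it is 50%.

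**4. Incomplete knowledge.** If the observer knows the block position but sees each earlier randomized assignment only with probability k, certainty requires having seen both patients in the exhausted arm. The share at 30 becomes 31.1% × k²: 17.5% at k = 0.75, 7.8% at 0.50 and 1.9% at 0.25. The documents do not give k.

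**5. Possible effect on the primary rule (illustration only).** Let agreement be p when the next slot is uncertain and q when it is certain. A refused slot stays open for the next patient. The values of q are assumptions, because the documents give none.

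| p | q | P(at least 26 of 50) |
|---|---|---|
| 60% | 60% | 90% |
| 60% | 50% | 78% |
| 60% | 40% | 56% |
| 60% | 70% | 95% |
| 40% | 40% | 6% |
| 40% | 60% | 19% |

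**6. Alternatives at 30 randomized.** The observer is assumed to know the rule and all earlier randomized assignments.
- *Blocks of 4, 6 and 8 chosen at random, current size unknown (simulation):* about 2% certain, best guess about 67%.
- *Big stick, limit 3:* each assignment is a fair toss unless the imbalance is 3, when the next is forced. The expected number of forced assignments is 4.56, and 4.56/30 = 15.2%. Best guess: 0.152 + 0.5 × 0.848 = 57.6%.

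**The case against.** The strongest reply is that the one-third figure needs an observer whom the documents do not describe. Randomized patients and choosers receive the same two regimens, so seeing a patient on lower-dose G-CLAM does not show that a slot was used. The observer must also know each patient's randomization status and the order. Step 4 shows how quickly certainty falls without that knowledge. This stands: about 31% is an upper limit.

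Second, a physician with a strong preference has little need to predict, because a patient who declines can openly receive the preferred arm. Influence through discussion exists under any allocation method, and the study sets out to observe it. This also stands in part. It weakens the incentive, but it does not remove the case of a physician who is comfortable with randomization only when the next slot looks acceptable.

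Third, the trial is not powered for arm comparisons (14.3.2), and first-stage accrual for the within-arm rules may be non-randomized (14.4). That limits the harm to the between-arm monitoring, although that monitoring can still close an arm.

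Section 16.3 forbids selectivity, but only in offering the study. It does not cover agreement to be randomized.

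**Conclusion.** The point holds as a risk that the stated scheme permits. A fully informed observer could know up to about 31% of assignments at 26 to 30 randomized patients (33% in complete blocks) and could guess about 70% correctly. This could influence the agreement proportion, in an unknown direction, and could select patients into the early-death and MRDneg CR comparison.

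A reader might infer more in two ways, and the documents support neither.
- *That physicians will in fact know a third of assignments.* The documents do not say what individual oncologists see or who holds the list. Concealment in practice is possible even though the plan does not describe it.
- *That the primary endpoint is biased.* No steering is shown, the agreement rates in step 5 are assumed, and opposite steering by arm could cancel in the overall proportion.

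The change is worth making because it costs little and protects the endpoint that carries the study's decision rule.

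**What to change.** In section 14.1, remove the block size. State that the restriction method and its parameters are held in a restricted randomization file not available to treating physicians. In that file, specify one of:

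- **Randomly varying blocks, for example 4, 6 and 8.** This almost removes certainty (about 2%) but barely lowers best-guess accuracy (about 67%, against 70% now).
- **A big-stick rule with maximum imbalance 3.** This leaves more certain assignments (about 15%) but makes the rest fair tosses (best guess about 58%).

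The choice depends on whether certain knowledge or general guessability is the greater worry. Requiring the Appendix D answer to be recorded before the assignment is issued would not solve this problem, because the deduction from past assignments can be made before the patient answers.

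The cost is an edit to 14.1 and a regenerated list. Sample size, endpoint and treatment are unchanged. The final difference between randomized arms could reach 4 with blocks up to 8, or 3 with the big-stick rule, against 2 with blocks of 4. This matters little in a study not powered to compare arms.

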14.2 Sample Size and Power

This study will enroll up to 50 subjects.

14.3 Primary/Exploratory Endpoints/Hypotheses and Analytical Methods

14.3.1 Primary endpoint

The primary objective of this study is to evaluate the feasibility of randomizing patients to either intensive or non-intensive induction and post remission chemotherapy. We will consider randomization feasible (i.e. a subsequent, larger study would be designed as a randomized trial) if the true proportion of patients willing to be randomized is 60% or higher. With 50 patients in a feasibility study and accounting for the sample variation associated with 50 patients, we will consider randomization feasible if at least 52% of the patients agree to be randomized (i.e. 26 or more of 50 patients agree to be randomized). If the true proportion willing to be randomized is 60%, the probability of observing 52% or more willing to be randomized is 90%. The probability of having 26 or more of the 50 patients agree to be randomized is only 6% if the true randomization agreement rate is 40%, and <1% if the true randomization agreement rate is 30% or lower, providing good operating characteristics not only to avoid a false negative result but also a false positive result. If one treatment arm closes prematurely (see section on monitoring below), we will conclude that randomization is not feasible, and the remaining patients will be treated on the remaining arm. Continuation of enrollment into that remaining arm will allow us to gain additional experience and provide more precise estimates of treatment efficacy and treatment-related toxicities.

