Since 2012, we have used G-CLAM extensively in adults with newly diagnosed AML and high-grade MDS, primarily as part of a large, ongoing institutional phase 1/2 trial (FHCRC #2734.00). Our interest in this regimen stems from data indicating improved anti-leukemic activity with regimens containing cladribine, high-dose cytarabine, and escalated doses of mitoxantrone compared to standard 7+3 chemotherapy. Data from this trial, which was presented at the 2016 annual meeting of the American Society of Hematology, have established the safety of a G-CLAM regimen with escalated doses of mitoxantrone, which will form the basis for the backbone used in this proposal. Specifically, the phase 1 portion on 33 patients established the highest dose tested (mitoxantrone at 18 mg/m²/day) as the maximally tolerated dose. A total of 62 patients, including 6 treated in phase 1, received G-CLAM at MTD. Patient characteristics were as follows: median age 58 (21-81) years, median TRM score 2.85 (0.06-6.73), with AML (n=52) or high-risk MDS (n=10). Cytogenetics were favorable in 6, intermediate in 44, and adverse in 12 (MRC criteria); 11 patients had NPM1 and 6 had FLT3 mutations. Fifty-two patients (83.9%, 95% confidence interval: 72.3-92.0%) achieved a CR (n=48 [77.4%: 65.0-87.1%]), or CRp/i (n=4 [6.5%: 1.8-15.7%]) with 1-2 cycles of therapy. Only 3 patients required 2 cycles to best response. Among the 48 CR patients, 43 (89.6%) were negative for measurable residual disease (MRD^{neg}) by flow cytometry. Four patients had morphologic leukemia free state, 1 patient with myeloid sarcoma had a partial remission, 4 had resistant disease, and 1 died from indeterminate cause. One patient died within 28 days of treatment initiation (septic shock). Median times to an absolute neutrophil count \geq 500/ μ L and a platelet count of \geq 50,000/ μ L were 26 and 23 days. Besides infections and neutropenic fever, maculopapular rash, and hypoxia (fluid overload/infection-related) were the most common grade \geq 3 adverse events. In addition to the phase 1/2 MTD cohort, there were 15 patients treated in an expansion cohort and 3 eligible patients treated off protocol with mitoxantrone at 18 mg/m². For these 80 patients combined treated at MTD, the CR and CR/CRp/i rates were 76.3% and 81.2%. After multivariable adjustment, compared to 300 patients treated with 7+3 on the SWOG S0106 trial, G-CLAM with mitoxantrone 18mg/ m² was associated with an increased probability of CR (odds ratio [OR]= 3.08, p=.02), CR/CRp/i (OR=2.96, p=.03), a trend towards improved MRD^{neg} CR (OR= 3.70, p=.06), and a trend towards improved overall survival ([OS]; hazard ratio=0.34, p=.07). For the entire study cohort, the 6 and 12-month relapse-free survival were 73% (64-83%) and 62% (42-74%) and the 6 and 12-month OS were 89% (82- 96%) and 77% (67-88%). Together, our study found G-CLAM with mitoxantrone up to 18 mg/m²/day to be well tolerated and to have potent anti-leukemia activity.

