14.4 Monitoring for efficacy and early mortality

This study will evaluate each regimen separately, and also compare regimens among patients who are randomized. Details for both sets of analyses are provided below.

Within-arm monitoring for efficacy and early mortality

We will enroll patients in 2 stages in order to allow for early stopping for unacceptable differences in early mortality or inefficacy. Early mortality will be defined as death for any reason on or before day 28 after starting therapy. Inefficacy will be evaluated using MRD^{neg} CR.

We will use our ongoing clinical trial using a CPX-351 in medically less fit adults with AML or high-grade MDS will provide “historical” control data for both inefficacy and early mortality. In this trial (FHCRC #2642.00), which used essentially identically inclusion/exclusion criteria, we have so far treated 37 subjects at a CPX-351 dose of 32 units/m². Among these, 8 patients achieved an MRD^{neg} CR (22%). Ten patients (27%) died within 28 days of treatment initiation; at least 4 of these subjects experienced early disease progression as main cause of death, highlighting the balance between treatment efficacy and potential toxicity.

In the first stage, 10 patients will be accrued to each arm, either in a randomized or non-randomized fashion. Each arm will be evaluated separately for early death and inefficacy stopping rules. Accrual may temporarily be held while outcome data on these patients matures.. As some patients may choose to not be randomized, the 2 treatment arms may be evaluated at a different time point for early stopping.

1) Lower-dose Arm: After 10 patients have been accrued to the lower-dose arm, we will evaluate for early death and inefficacy.

Early death: If the number of early deaths is 5 or higher, accrual will stop with the conclusion that the arm is too toxic for further randomization. If the true early mortality rate is 30% or less, the probability of observing 5 or more early mortality events is 15%.

Inefficacy: If there are 0 patients with MRD^{neg} CR, accrual will stop with the conclusion that the arm is not efficacious enough for further randomization. If the true MRD^{neg} CR rate is 22%, the probability of observing 0 MRD^{neg} CRs in 10 patients is 8%.

2) Higher-dose Arm: After 10 patients have been accrued to the higher dose arm, we will evaluate for early death and inefficacy.

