Early death: If the number of early deaths is 5 or higher, accrual will stop with the conclusion that the arm is too toxic for further randomization. If the true early mortality rate is 30% or less, the probability of observing 5 or more early mortality events is 15%.

Inefficacy: If there are 0 patients with MRD^{neg} CR, accrual will stop with the conclusion that the arm is not efficacious enough for further randomization. If the true MRD^{neg} CR rate is 22%, the probability of observing 0 MRD^{neg} CRs in 10 patients is 8%.

Between-arm monitoring for efficacy and early mortality

After enrollment of at least 10 patients in each arm (at which point one arm may have more than 10 patients accrued due to slower accrual in one arm), we will compare the two arms for relative mortality and efficacy. If, based on Fisher's exact test, the early mortality rate is significantly higher in one arm at the alpha =10% level (this criterion will be met if, for example, both arms have accrued 10 patients one arm has 0 early mortality events and the other arm has 4), accrual will stop in that arm with the conclusion that the arm with the higher early mortality rate is too toxic for further randomization. In addition, if based on Fisher's exact test, the MRD^{neg} CR rate is significantly higher in one arm compared to the other at the alpha = 10% level (for example, this criterion will be met if both arms have accrued 10 patients and one arm has 2 MRD^{neg} CRs and the other has 7), the accrual will stop in that arm with the conclusion that the arm with the lower MRD^{neg} CR rate is not efficacious enough for further randomization.

If accrual does not stop in both arms, up to a total of 50 patients will be accrued.

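### The 90% chance of concluding that randomization is feasible ignores the early-closure condition; under the full rule it is about 56–61% at the plan's own reference rates

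*Combined protocol and SAP*

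**What the plan says.** Section 14.3.1 (Primary endpoint) sets the threshold at 26 of 50 patients agreeing to randomization. For a true willingness of 60% it states: "If the true proportion willing to be randomized is 60%, the probability of observing 52% or more willing to be randomized is 90" per cent. It gives 6% for reaching 26 when true willingness is 40%, and <1% at 30% or lower. It describes these figures as "providing good operating characteristics not only to avoid a false negative result but also a false positive result". The next sentence adds a second condition: "If one treatment arm closes prematurely (see section on monitoring below), we will conclude that randomization is not feasible". Remaining patients are then treated on the arm still open.

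Section 14.4 says how an arm can close. At 10 patients, each arm stops for 5 or more deaths by day 28, or for no MRD-negative CR. For the first: "If the true early mortality rate is 30% or less, the probability of observing 5 or more early mortality events is 15" per cent. For the second: "If the true MRD^{neg} CR rate is 22%, the probability of observing 0 MRD^{neg} CRs in 10 patients is 8" per cent. Once both arms have at least 10 patients, Fisher's exact test at 10% compares them on early death and on MRD-negative CR; for the latter, "this criterion will be met if both arms have accrued 10 patients and one arm has 2 MRD^{neg} CRs and the other has 7". The historical control is 37 patients on another regimen, of whom 8 (22%) had an MRD-negative CR; on early death, "Ten patients (27%) died within 28 days of treatment initiation".

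Neither section combines the closure probabilities with the agreement count.

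**The concern.** The conclusion that randomization is feasible needs two things: enough patients agree, and neither arm closes early. The three printed probabilities are binomial tails for the first condition only, yet the paragraph uses them to claim protection against a false-negative conclusion. With a 15% and an 8% closure risk in each of two arms at the plan's own rates, plus the between-arm tests, 90% cannot be the chance of concluding feasible.

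This conclusion decides whether the next, larger study is designed as a randomized trial. A reader will take 10% as the risk of wrongly ruling that out when 60% are willing. A closure also ends the choice between arms, so 26 of 50 can no longer be assessed. A not-feasible result could then be read as evidence about willingness when it came from clinical outcomes in about 10 patients per arm.

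**Working it through.** **Step 1: the plan's figures.** With X binomial(50, p), P(X ≥ 26) is 0.9022 at p = 0.60, 0.0573 at 0.40 and 0.0009 at 0.30. The stated 90%, 6% and <1% reproduce. So do the stopping figures: with 10 patients, P(≥ 5 deaths) at 30% is 0.1503, and P(no MRD-negative CR) at 22% is 0.78^10 = 0.0834.

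**Step 2: sidedness of the Fisher tests.** The plan's examples fit a two-sided test at 10%. For 0/10 v 4/10, p = 0.087, while 0 v 3 gives 0.21. For 2/10 v 7/10, p = 0.070, while 2 v 6 gives 0.17. A one-sided test would already stop at 2 v 6 (p = 0.085).

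**Step 3: probability that an arm closes.** Each patient has an early death, an MRD-negative CR, or neither (trinomial), and all outcomes in 10 + 10 patients are enumerated exactly. At 30%/22%:

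- One arm closes on its own rules: 0.1503 + 0.0834 − 0.0274 (both stops met) = 0.206, so it stays open with probability 0.794.
- Both arms stay open: 0.794² = 0.630.
- Both stay open after the between-arm tests as well: 0.616.
- At least one closure: 1 − 0.616 = 38.4%, although the arms do not truly differ.

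At 27%/22% the corresponding values are 0.833, 0.694 and 0.677, with closure in 32.3%.

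**Step 4: joint probability.** P(feasible) = P(X ≥ 26) × P(no closure). At 60% willing this is 0.902 × 0.616 = 55.6% at 30%/22%, and 0.902 × 0.677 = 61.0% at 27%/22%.

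| Early death / MRD-negative CR, both arms | Source | At least one arm closes | P(feasible), 60% willing |
|---|---|---|---|
| 31% / 22% | Appendix A, TRM probability above the 13.1 cut-off (older data); section 14.4 | 40.7% | 53.5% |
| 30% / 22% | rates used for the stopping rules | 38.4% | 55.6% |
| 27% / 22% | historical control | 32.3% | 61.0% |
| 20% / 30% | assumed | 14.5% | 77.2% |
| 15% / 40% | assumed | 7.6% | 83.3% |
| 10% / 50% | assumed | 5.2% | 85.5% |
| 1/62 / 43/62 | G-CLAM in fit adults, section 1.0 | 3.7% | 86.8% |

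The last row is an extreme bound. Section 1.0 reports one death within 28 days among 62 patients, and "Among the 48 CR patients, 43 (89.6%) were negative for measurable residual disease". Their median TRM score was 2.85; this trial requires at least 13.1.

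**Step 5: other willingness rates**, from 30%/22% to 27%/22%: 44–48% at 55% willing, 27–30% at 50%, 3.5–3.9% at 40%, and below 0.1% at 30%. Even if every patient were willing, P(feasible) at 30%/22% would be 61.6%.

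**Step 6: sensitivity at 60% willing**, for 30%/22% and 27%/22%:

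- within-arm rules only, no Fisher tests: 56.8% and 62.6%
- death and CR treated as independent: 53.5% and 59.4%
- Fisher look at 10 v 14 patients (simulation): 54.3% and 59.6%
- Fisher tests among randomized patients only (simulation): about 54% and 60%

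**The case against.** The strongest reply is that nothing printed is miscalculated. Each sentence names its own event, the claim of good operating characteristics ends the sentence about the count, and the closure condition follows with a pointer to section 14.4, where the 15% and 8% appear. On that reading the plan omits a joint probability but misstates nothing. The arithmetic part stands. But the claim concerns false results of the feasibility conclusion, and the next sentence gives that same conclusion a second route to failure.

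A second reply is that closure is not a false negative about willingness: section 14.4 records it as toxicity or inefficacy, and patient and physician surveys collect preferences separately. That is true of the data. The primary conclusion is nevertheless the same for either cause, and no separate estimate of willingness with an interval is specified.

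A third concerns the inputs. Section 14.4 words the death rate as an upper limit of 30%, the historical control is a different drug, and no expected rate is given for either G-CLAM arm in less fit patients. This is fair, and it is why a range is needed. The better rates are assumptions, apart from the fit-adult row. With the within-arm rules alone, 10%/50% gives 89.8% and the fit-adult rates 90.2%, so at very good rates the whole shortfall comes from the Fisher tests. Section 14.4 also refers to comparing regimens among randomized patients, but restricting the tests to them barely moves the results. None of this restores 90% at the plan's own reference rates.

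**Conclusion.** The concern holds. The printed 90%, 6% and <1% are right for the agreement count, but they are not properties of the two-condition rule in the same paragraph. At 60% willing, the chance of a not-feasible conclusion is about 39–44% at the plan's reference rates and about 13–23% at the better rates examined, against the 10% a reader would infer. The error is on the false-negative side only: the closure condition lowers the false-positive risk at 40% willing from 5.7% to 3.5–3.9%.

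The main figures assume equal true rates in both arms, willingness independent of outcome, early death and MRD-negative CR mutually exclusive, and the between-arm look at 10 v 10. The variations above move the reference-rate results only within about 53–63%. If the arms truly differ, the probability can be lower: about 50% with 20%/20% in one arm and 30%/50% in the other.

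**What to change.** Keep the decision rule and the stopping rules, and change the text of section 14.3.1 in three ways.

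1. State that 90%, 6% and <1% refer to the agreement count alone.
2. Replace the clause on good operating characteristics with joint probabilities over a range of arm rates, with the assumptions listed. At 60% willing: about 56% (30%/22%), 61% (27%/22%), 77% (20%/30%), 83% (15%/40%) and 86% (10%/50%). For 30%/22% to 27%/22%: 44–48% at 55% willing, 27–30% at 50% and 3.5–3.9% at 40%. Mark the rates that are assumed.
3. Report the proportion willing among patients asked while both arms were open, with an exact 95% confidence interval and no pass/fail threshold, separately from any arm closure. For example, closure after 20 patients with 12 willing would give 60% (36% to 81%).

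The cost is some wording and a short table. Patients, treatment and data collection are unaffected. The one drawback is that the stated chance of concluding feasible becomes less favourable.
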